## 4. SUBJECT DISPOSITION

### 4.1. Subject Enrollment and Disposition

A summary of subject enrollment will be provided for each investigator within Japan by treatment group within each cohort and overall. The summary will present the number and percentage of subjects in the Safety Analysis Set. For each column, the denominator for the percentage calculation will be the total number of subjects analyzed for that column.

For Cohort 1, a similar enrollment table will be provided by randomization stratum for each treatment group and overall. The denominator for the percentage of subjects in the stratum will be the total number of subjects in the Safety Analysis Set in Cohort 1 within that stratum for each treatment group and overall. If there are discrepancies in the value used for stratification assignment between the IWRS and the clinical database including CRF and laboratory data, the value collected in the clinical database will be used for the summary. A listing of subjects with the IWRS randomization strata that differ from stratification factor data entered in the clinical database at the time of data finalization will be provided.

The randomization schedule used for the study will be provided as an appendix to the CSR.

A summary of subject disposition will be provided by treatment group and overall for each cohort. This summary will present the number of subjects screened, the number of subjects randomized/enrolled, the number of subjects randomized/enrolled but never treated, and the number and percentage of subjects in each of the categories listed below. For the “Treated” category, the denominator for the percentage calculation will be the total number of subjects enrolled for each column. For all other categories, the denominator for the percentage calculation will be the total number of subjects in the Safety Analysis Set for each column.

- Treated (Safety Analysis Set)
- In FAS
- Continuing study treatment if applicable
- Completed study treatment
- Did not complete study treatment with reasons for premature discontinuation of study treatment
- Completed study
- Did not complete the study with reasons for premature discontinuation of study

Among subjects who completed study treatment and who discontinued study treatment, the number and percentage of subjects will be summarized for:

- Who had no HCV posttreatment Week 4 assessment and thereafter (No HCV FU-4 and thereafter)
- Who had HCV posttreatment Week 4 assessment but no HCV posttreatment Week 12 assessment and thereafter (With HCV FU-4 but No FU-12 and thereafter)

If a subject did not have any HCV RNA assessment  $\geq$  21 days after the last dose of any study drug (ie, lower bound of FU-4 visit for HCV RNA data), the subject is categorized as having “No HCV FU-4 and thereafter”. If a subject had the HCV FU-4 assessment but did not have any HCV RNA assessment  $\geq$  70 days after the last dose of any study drug (ie, lower bound of FU-12 visit for HCV RNA data), the subject is categorized as having “With HCV FU-4 but No FU-12 and thereafter”.

In addition, the total number of subjects who were randomized, and the number of subjects in each of the disposition categories listed above will be depicted by a flowchart.

The following by-subject listings will be provided by subject ID number in ascending order to support the above summary tables:

- Disposition for subjects who complete study treatment and study
- Disposition for subjects who did not complete study treatment and/or study with reasons for premature discontinuation of study treatment and/or study
- Lot number and kit ID (if applicable)

#### **4.2. Extent of Exposure**

Extent of exposure to study drug will be examined by assessing the total duration of study drug exposure and the level of adherence to the study drug regimen specified in the protocol.

##### **4.2.1. Duration of Exposure to Study Drug**

Total duration of exposure to study drug will be defined as last dose date minus first dose date plus 1, regardless of any temporary interruptions in study drug administration, and will be expressed in weeks using up to 1 decimal place (eg, 4.5 weeks).

The total duration of exposure to study drug will be summarized using descriptive statistics (n, mean, SD, median, Q1, Q3, minimum, and maximum) and using the number (ie, cumulative counts) and percentage of subjects exposed through the following time periods: baseline (Day 1), Week1 (Day 7), Week 2 (Day 14), Week 3 (Day 21), Week 4 (Day 28), Week 5 (Day 35), Week 6 (Day 42), Week 8 (Day 56), Week 10 (Day 70), and Week 12 (Day 84). A 3-day window will be applied to the last planned on-treatment visit to match with the protocol-

specified visit window (ie, the number of subjects exposed through week 12 will be calculated as the number of subjects who were exposed to study drug for at least 81 days). Summaries will be provided by treatment group within each cohort for the Safety Analysis Set.

#### **4.2.2. Adherence to Study Drug**

The total number of tablets administered will be summarized using descriptive statistics (n, mean, SD, median, Q1, Q3, minimum, and maximum).

The presumed total number of tablets administered to a subject will be determined by the data collected on the drug accountability CRF using the following formula:

$$\begin{aligned} \text{Total Number of Doses Administered} = \\ (\sum \text{No. of Tablets Dispensed}) - (\sum \text{No. of Tablets not administered}) \end{aligned}$$

The level of adherence to the study drug regimen will be assessed based on the total amount of study drug administered relative to the total amount of study drug prescribed at baseline.

The level of adherence will be expressed in percentage using the following formula:

$$\text{Level of Adherence (\%)} = \left( \frac{\text{Total Amount of Study Drug Administered}}{\text{Total Amount of Study Drug Prescribed at baseline}} \right) \times 100$$

Note: If calculated adherence is greater than 100%, the result will be set to 100%.

In Cohort 1, for Group 1, the total amount of LDV/SOF (90 mg/400 mg) prescribed for 12 weeks would require 84 tablets; for Group 2, the total amount of SOF (400 mg) prescribed for 12 weeks would require 84 tablets and weight-based RBV (200 mg) prescribed for 12 weeks would require 252 (3 tablets/day for baseline weight  $\leq$  60 kg) or 336 (4 tablets/day for baseline weight  $>$  60 kg to  $\leq$  80 kg) tablets or 420 (5 tablets/day for baseline weight  $>$  80 kg) tablets.

In Cohort 2, the total amount of LDV/SOF (90 mg/400 mg) prescribed for 12 weeks would require 84 tablets.

Subjects who prematurely discontinue study drug for lack of efficacy (ie, virologic failure) will have the total amount of study drug prescribed calculated up to the first date when virologic failure criteria were met. For virologic failure confirmed by 2 consecutive measurements the date of the first measurement will be used. If there are study drug bottles dispensed on or after the subject first met virologic failure criteria, these bottles will not be included in the calculation of adherence. If a bottle is dispensed and the bottle is returned empty, then the number of tablets returned will be entered as zero. If a bottle is dispensed but not returned (missing), the number of tablets taken from that bottle will be counted as zero.

Descriptive statistics for the level of adherence (n, mean, SD, median, Q1, Q3, minimum, and maximum) with the number and percentage of subjects belonging to adherence categories (eg,  $<$  80%,  $\geq$  80 to  $<$  90%,  $\geq$  90%) will be provided by treatment group for the Safety Analysis

Set for both cohorts. Categorical displays will be provided for the number of subjects who are at least 80% adherent to their drug regimen for both cohorts and all drugs (ie, adherence is  $\geq 80\%$  for each of the study drugs).

No inferential statistics will be provided for duration of exposure and adherence to study drug.

A separate by-subject listing of study drug administration and drug accountability will be provided by subject ID number (in ascending order) and visit (in chronological order).

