#### 7.5. Toxicity Management

#### 7.5.1. **RBV Dose Adjustments (Only Cohort 1)**

Dose reduction or discontinuation of RBV due to toxicity should be performed according to the Japanese Rebetol® product label. Information is provided in Table 7-1 and Table 7-2.

In the event a female partner of a male subject becomes pregnant, the male subject must permanently discontinue SOF and RBV.

Test items	Value	Ribavirin		
Neutrophil count	< 500 /mm 	Discontinue		
	< 50,000 /mm 	Discontinue		
Platelet count	< 25,000/mm 	Discontinue (resumption of dosing not allowed)		
Hemoglobin level (No cardiac disease or history of cardiac disease)	< 10 g/dL	Reduce dose $600 \text{ mg/day} \rightarrow 400 \text{ mg/day}$ $800 \text{ mg/day} \rightarrow 600 \text{ mg/day}$ $1,000 \text{ mg/day} \rightarrow 600 \text{ mg/day}$		
, ,	< 8.5 g/dL	Discontinue		
Hemoglobin level (Cardiac disease or history of	< 10 g/dL, or during administration, reduction of 2 g/dL or more relative to Day 1 persists for 4 weeks	Reduce dose $600 \text{ mg/day} \rightarrow 400 \text{ mg/day}$ $800 \text{ mg/day} \rightarrow 600 \text{ mg/day}$ $1,000 \text{ mg/day} \rightarrow 600 \text{ mg/day}$		
cardiac disease present)	< 8.5 g/dL, or after dose reduction, less than 12 g/dL even after 4 weeks	Discontinue		

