#### Table 7-1. RBV Dose Reduction Guidelines for Non-Cirrhotic Subjects

Source: Japan Rebetol® Product Label {MSD K.K. Kudan-kita Chiyoda-ku 2015}

Test items	Value	Ribavirin
Neutrophil count	< 500 /mm 	Discontinue
	< 50,000 /mm 	Discontinue
Platelet count	< 25,000/ mm 	Discontinue (resumption of dosing not allowed)
Hemoglobin level	<pre>< 11 g/dL at Week 1 to 4 after start</pre>	Reduce dose 600 mg/day → 400 mg/day
Hemoglobin level (No cardiac disease or history of cardiac disease)	< 10 g/dL at Week 5 to 12 after start of administration	$800 \text{ mg/day} \rightarrow 600 \text{ mg/day}$ 1,000 mg/day $\rightarrow 600 \text{ mg/day}$
	< 8.5 g/dL	Discontinue
	< 11 g/dL at Week 1 to 4 after start of administration or during administration, reduction of 2 g/dL or more relative to Day 1 persists for 4 weeks	Reduce dose 600 mg/day → 400 mg/day
Hemoglobin level (Cardiac disease or history of cardiac disease present)	< 10 g/dL at Week 5 to 12 after start of administration or during administration, reduction of 2 g/dL or more relative to baseline persists for 4 weeks	800 mg/day $\rightarrow$ 400 mg/day 1,000 mg/day $\rightarrow$ 600 mg/day
	< 8.5 g/dL, or after dose reduction, less than 12 g/dL even after 4 weeks	Discontinue

Table 7-2.RBV Dose Reduction Guidelines for Cirrhotic	Subjects
---	-----------------

Source: Japan Rebetol® Product Label {MSD K.K. Kudan-kita Chiyoda-ku 2015}

Once RBV has been withheld due to either a laboratory abnormality or clinical manifestation, an attempt may be made to restart RBV at a lower daily dose with subsequent step-wise increase in the daily dose as clinically indicated. However, it is not recommended that the RBV daily dose be increased to the original assigned dose.

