## 7.5.2. Subject Stopping Rules

The Medical Monitor must be consulted prior to dose discontinuation of LDV/SOF FDC or SOF unless the investigator believes that immediate action is warranted to ensure the continued safety of the subject.

Due to a clinical or laboratory event, administration of all study drug(s) may be discontinued. There is no option for LDV/SOF FDC or SOF dose reduction. If LDV/SOF FDC or SOF is stopped due to toxicity, it must not be restarted. If SOF is discontinued then RBV must also be discontinued. If RBV is discontinued permanently, then SOF must also be discontinued. In these cases that study drug(s) are discontinued permanently, the subject must complete an ET visit. Posttreatment 4-Week, 12-Week and 24-Week visits must also be scheduled, 4, 12 and 24 weeks from the last dose of study drug.

Subjects who meet any of the following laboratory criteria must stop all study medication(s):

- Elevation of ALT and/or AST above the upper limit of normal and > 5x Day 1 or nadir, confirmed by immediate repeat testing
- Abnormal elevation of ALT > 3 x Day 1 *and* total bilirubin > 2 x ULN, confirmed by immediate repeat testing
- Elevation of ALT > 15 x ULN, confirmed by immediate repeat testing
- Any Grade 3 or greater rash associated with constitutional symptoms
- Any Grade 4 adverse event or laboratory abnormality assessed as related to LDV/SOF FDC or SOF

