### **3.4. Examination of Subject Subsets**

Subsetting of subjects based on randomization stratification factors will be explored for subgroup analyses. If there are discrepancies in stratification factor values between the IWRS and the clinical database, the values recorded in the clinical database will be used for analyses.

Other subject subsets will also be explored for the primary efficacy endpoint (SVR12), including the following:

- age (< 65 years,  $\geq$  65 years)
- sex (male, female)
- baseline BMI ( $< 25 \text{ kg/m}^2$ ,  $\geq 25 \text{ kg/m}^2$ )
- HCV genotype subtype (if applicable)
- cirrhosis (cirrhosis, absence of cirrhosis, missing)

- IL28B (CC, non-CC; with non-CC further broken down to CT, TT)
- Baseline HCV RNA (< 800,000 IU/mL,  $\geq$  800,000 IU/mL, and  $< 5 \log_{10}$  IU/mL,  $\geq 5 \log_{10}$  IU/mL)
- baseline alanine aminotransferase (ALT) ( $\leq 1.5 \times$  upper limit of normal [ULN],  $> 1.5 \times$  ULN)
- prior HCV treatment experience (treatment naive, treatment-experienced)
- most recent prior HCV treatment response (non-responder, relapse/breakthrough, early treatment discontinuation, met a virologic stopping rule, not otherwise listed, unknown) for treatment-experienced subjects
- completed study treatment, discontinued study treatment
- adherence to study regimen (<80%,  $\geq$  80%)

The primary efficacy endpoint for Cohort 2 will be examined using the applicable subsets above.

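### RBV adherence is scored against the starting dose, and SVR12 is then compared between arms within two subgroups that form after randomisation

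*SAP*

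**What the plan says.** - **Adherence measure.** SAP 4.2.2 takes the amount administered "relative to the total amount of study drug prescribed at baseline". For RBV the 12-week totals are fixed by baseline weight at 252, 336 or 420 units of 200 mg. The only stated adjustment to the denominator is for subjects who stop because of virologic failure.
- **Regimen rule.** The same section counts subjects who are "at least 80% adherent to their drug regimen for both cohorts and all drugs", meaning that each drug must reach 80%.
- **RBV dose changes.** Protocol 7.5.1: "Dose reduction or discontinuation of RBV due to toxicity should be performed according to the Japanese Rebetol" product label, with the steps in Tables 7-1 and 7-2. Some triggers act early. One haemoglobin criterion for cirrhotic subjects in Table 7-2 begins "< 11 g/dL at Week 1 to 4 after start of administration or during administration".
- **The other drugs.** Protocol 7.5.2: "There is no option for LDV/SOF FDC or SOF dose reduction". It also states: "If RBV is discontinued permanently, then SOF must also be discontinued".
- **Subgroups.** SAP 3.4 lists "adherence to study regimen" (below 80%, or 80% and above) and completed versus discontinued treatment among the SVR12 subsets. SAP 6.1.4 asks, in Cohort 1, for the Group 1 minus Group 2 difference with an exact 95% CI in every Section 3.4 subgroup, and for a forest plot of them.

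**The concern.** SAP 4.2 sets out to measure adherence to the regimen that the protocol specifies. For RBV that regimen includes directed reductions, yet a subject who follows one exactly is scored as having missed doses. The denominator is already cut short for virologic failure, another stop that the protocol requires, but RBV reductions have no equivalent.

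This reaches efficacy through the subgroups. Adherence and completion are both known only after randomisation. In SOF+RBV, the below-80% group can mix missed doses with RBV toxicity, and the discontinued group can include subjects who stopped SOF because RBV was stopped for good. LDV/SOF subjects can miss tablets or stop early, but not for either of these reasons. A difference between arms in these rows therefore mixes the treatment effect with who was reduced or stopped for RBV toxicity. On the forest plot the rows would sit beside baseline subgroups such as age and sex, with nothing to mark them as different.

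**Working it through.** **Reproducing the SAP totals.** Units per day × 84 days: 3 × 84 = 252, 4 × 84 = 336, 5 × 84 = 420. These match SAP 4.2.2.

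**Score of a subject who takes everything prescribed.** Let *f* be the full and *r* the reduced number of 200 mg capsules per day, and *d* the number of full-dose days. Assume one permanent reduction held to day 84, with no interruption. Then

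adherence = [*f·d* + *r*·(84 − *d*)] / (84·*f*).

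The steps come from Protocol Tables 7-1 and 7-2. Solving for the 80% cut-off:

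| Step (mg/day) | *f* to *r* | Lowest possible (*d* = 0) | Last *d* below 80% | Next day |
|---|---|---|---|---|
| 600 to 400 | 3 to 2 | 66.7% | 33 (201/252 = 79.76%) | 202/252 = 80.16% |
| 800 to 600 | 4 to 3 | 75.0% | 16 (268/336 = 79.76%) | 269/336 = 80.06% |
| 1,000 to 600 | 5 to 3 | 60.0% | 41 (334/420 = 79.52%) | 336/420 = 80.00% |
| 800 to 400 | 4 to 2 | 50.0% | 50 (268/336 = 79.76%) | 270/336 = 80.36% |

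Taking the nominal visit day as the number of full-dose days, the crossing falls between these visits:

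| Step (mg/day) | Below 80% | At or above 80% |
|---|---|---|
| 600 to 400 | Week 4: 196/252 = 77.8% | Week 5: 203/252 = 80.6% |
| 800 to 600 | Week 2: 266/336 = 79.2% | Week 3: 273/336 = 81.3% |
| 1,000 to 600 | Week 5: 322/420 = 76.7% | Week 6: 336/420 = 80.0% |
| 800 to 400 | Week 6: 252/336 = 75.0% | Week 8: 280/336 = 83.3% |

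So only early reductions reclassify a subject, and how early depends on the step.

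**Reach of the 800 to 400 step.** It stands only in the Table 7-2 row for cirrhotic subjects headed "Hemoglobin level (Cardiac disease or history of cardiac disease present", and applies to those over 60 and up to 80 kg. The Cohort 1 minimum of 20 cirrhotic subjects, split 1:1, gives about 20/2 = 10 in SOF+RBV, and the step covers only some of them.

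**With the denominator corrected.** For 600 to 400 after 28 days, the amount prescribed is 3 × 28 + 2 × 56 = 196. The score is 196/196 = 100%, against 77.8% as the SAP is written.

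**Size of the discontinued subgroup.** Non-completion in the studies cited in Protocol 1.2.2, with Clopper-Pearson limits:

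- SOF+RBV, genotype 2: 0/140, upper 95% limit 2.6%.
- LDV/SOF, genotype 1: 0/157, upper limit 2.3%.
- LDV/SOF for 12 weeks, genotype 2: 1/26 = 3.8% (0.1% to 19.6%).

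These bound the underlying rate, not the count in this trial. The discontinued row is likely to be small, but the documents do not fix how small. As an illustration with invented counts, 3/3 versus 3/3 under the exact method of SAP 6.1.4 gives limits of ±(1 − 0.025^(1/3)) = ±70.8 points.

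**The case against.** The strongest objection is that the link between the adherence score and the SVR12 subgroup is inferred. SAP 3.4 does not define regimen adherence for a two-drug arm, and the each-drug rule appears in SAP 4.2.2 for categorical exposure displays. If the subgroup were built on SOF alone, an RBV reduction would move nobody. This stands as a gap in definition. But the each-drug rule is the only regimen-level rule in the SAP, and the completed/discontinued comparison does not depend on it.

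Second, the baseline denominator is openly stated and is a legitimate measure of exposure. That is true, and it should be kept, but as dose intensity rather than adherence.

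Third, a reader can trace much of the cause elsewhere: AEs leading to RBV modification or interruption (SAP 7.1.6), reasons for stopping treatment (SAP 4.1), and the by-subject drug administration listing (SAP 4.2.2). This helps interpretation but does not make the between-arm difference valid.

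Fourth, the documents give no RBV reduction rate, the day thresholds assume one lasting reduction, and no decision rests on these rows. All of this is correct, and it limits the severity. Protocol 7.5.1 also allows RBV to be withheld, restarted lower and raised stepwise, so actual scores could lie on either side of those shown. The 800 to 400 step is read from a table with broken cells and should be checked against the original.

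**Conclusion.** The concern holds and is minor. As written, a SOF+RBV subject who takes every prescribed capsule can be scored below 80% after an early directed reduction. The plan then asks for between-arm SVR12 differences within two groupings that RBV toxicity can shape in one arm only.

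The 33, 16, 41 and 50-day cut-offs rest on the each-drug rule, full compliance and a single reduction held to day 84. The objection to between-arm rows in post-randomisation subgroups needs none of these assumptions. The number of subjects affected cannot be derived from the documents and could be nil. The primary non-inferiority analysis in the Full Analysis Set is unaffected.

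**What to change.** 1. **SAP 3.4 and 6.1.4.** Present SVR12 by adherence and by completed versus discontinued treatment as within-arm rates only, labelled as post-randomisation groupings. Remove their between-arm differences and forest-plot rows.
2. **SAP 4.2.2.** Compute RBV adherence against the amount prescribed over time, allowing for protocol-directed reductions and interruptions. Keep the ratio to the baseline prescription and call it dose intensity.
3. **Clarification (optional).** In SAP 3.4, refer to the each-drug rule in SAP 4.2.2 as the definition of regimen adherence.

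Items 1 and 3 are wording, with fewer rows to program. Item 2 adds some derivation work and assumes that RBV dose changes are recorded on the eCRF, which is not among the documents. If they are not, item 1 alone removes the between-arm comparison. No new visits are needed, and the primary analysis and the RBV dose rules stay as they are.

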#### 3.4.1. Virologic Response-Based Treatment Stopping Criteria

The following on-treatment Virologic Response-based Treatment Stopping Criteria will be utilized:

[figure not shown]
- Confirmed HCV RNA ≥ LLOQ after 2 consecutive HCV RNA < LLOQ
- Confirmed > 1 log10 increase in HCV RNA from nadir
- HCV RNA  $\geq$  LLOQ through 8 weeks of treatment

Confirmation should be performed as soon as possible and must occur no later than 2 weeks after an initial observation indicating virologic failure during the on-treatment phase.

Subjects who terminate study drug early due to virologic failure as defined above will complete the Early Termination (ET) visit and all posttreatment visits.

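### For subjects stopped for virologic failure between dispensing visits, the SAP's adherence formula can count tablets taken after its denominator has ended, and the 100% cap hides the excess

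*SAP*

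**What the plan says.** SAP 4.2.2 defines adherence as study drug administered divided by study drug prescribed at baseline. On the numerator it says: "The presumed total number of tablets administered to a subject will be determined by the data collected on the drug accountability CRF". The formula is tablets dispensed minus tablets not administered, with no cut-off on the date a tablet was taken. A note adds: "If calculated adherence is greater than 100%, the result will be set to 100" (percent).

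Subjects who stop early for virologic failure have their own rule. The denominator is shortened: such a subject "will have the total amount of study drug prescribed calculated up to the first date when virologic failure criteria were met". The date is then fixed: "For virologic failure confirmed by 2 consecutive measurements the date of the first measurement will be used". The numerator is partly trimmed to match. For bottles dispensed on or after that date, "these bottles will not be included in the calculation of adherence". The paragraph ends: "If a bottle is dispensed but not returned (missing), the number of tablets taken from that bottle will be counted as zero".

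Protocol 3.4.1 asks for confirmation as soon as possible and says it "must occur no later than 2 weeks after an initial observation indicating virologic failure". Protocol Appendix 2 schedules dispensing at Day 1, Week 4 and Week 8. Protocol 5.6 requires a pill count at every visit after Day 1.

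Adherence is reported in the categories below 80%, 80% to below 90%, and 90% or more (SAP 4.2.2). It is also an SVR12 subgroup cut at 80% (SAP 3.4).

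**The concern.** The denominator stops at the first failing sample. The numerator stops there only if a new bottle is dispensed at that visit. Otherwise the bottle in use was dispensed earlier, so it stays in the calculation, and tablets taken from it while confirmation is awaited are counted against days that the denominator has dropped. The ratio then rises above true adherence, and the cap removes the one visible sign of this, a value over 100%.

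The affected subjects are on-treatment virologic failures. For them, a reader of the adherence table will naturally ask whether doses were missed. A subject who took fewer than 80% of doses up to failure could appear in the 80%-or-more or 90%-or-more category.

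**Working it through.** **Inputs.** One LDV/SOF or SOF tablet daily for 12 weeks; RBV 3, 4 or 5 units daily by weight (SAP 4.2.2). Maximum lag from first failing sample to confirmation: 14 days (Protocol 3.4.1). Dispensing at Day 1, Week 4 and Week 8 (Protocol Appendix 2). Bottles of 30 tablets (Protocol 5.2.2 and 5.3.2).

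**The plan's own figures.** 12 × 7 × 1 = 84 tablets, and 84 × 3, 4, 5 = 252, 336, 420. All match SAP 4.2.2, so the full-course denominators are correct.

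**Formula.** Let d be the day of the first failing sample, a the subject's constant true adherence, and k the number of dosing days after d supplied by bottles dispensed before d. Then

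reported adherence = min(100%, a × (d + k) / d).

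The value of a at which the report reaches a cut c is c × d / (d + k).

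**Assumptions.** One bottle per dispensing visit; leftover tablets are not used once a new bottle is dispensed; dosing continues to the end of the lag. The documents give no laboratory turnaround time.

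**Results with a 14-day lag**

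| First failing sample | d | k | a reported as 100% | a reported as 90% | a reported as 80% | a = 75% is reported as | a = 60% is reported as |
|---|---|---|---|---|---|---|---|
| Week 2 | 14 | 14 | 50% | 45% | 40% | 100% | 100% |
| Week 3 | 21 | 7 | 75% | 67.5% | 60% | 100% | 80% |
| Week 4 | 28 | 0 | 100% | 90% | 80% | 75% | 60% |
| Week 5 | 35 | 14 | 71.4% | 64.3% | 57.1% | 100% | 84% |
| Week 6 | 42 | 14 | 75% | 67.5% | 60% | 100% | 80% |
| Week 8 | 56 | 0 | 100% | 90% | 80% | 75% | 60% |
| Week 10 | 70 | 14 | 83.3% | 75% | 66.7% | 90% | 72% |

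At Week 3 only 7 days leak in, because the Week 4 bottle is excluded. At Weeks 4 and 8 nothing leaks in, because the new bottle is dispensed on the failure date itself. At Week 10 a subject below 80% cannot reach 100% but can cross both the 80% and 90% cuts.

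**Shorter lags, Week 6 failure.** With 7 days, a = 75% gives 0.75 × 49/42 = 87.5% and a = 60% gives 0.60 × 49/42 = 70%. With 3 days, they give 0.75 × 45/42 = 80.4% and 0.60 × 45/42 = 64.3%.

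**Opposite direction.** A fully adherent Week 6 failure whose second bottle is not returned is credited with the first 28 days only: 28/42 = 66.7%.

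**How many subjects.** Protocol 1.2.2.2 reports 140 subjects on SOF+RBV, all completing treatment, with all 5 failures being relapses. That is 0/140 on-treatment failures, with an upper 97.5% bound of 1 − 0.025^(1/140) = 2.6%. For 12-week LDV/SOF in genotype 2, Protocol 1.2.2.4 reports none among 26. The same formula gives 1 − 0.025^(1/26) = 13.2%, a much weaker bound. The 8-week group had one breakthrough among 27.

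**The case against.** The strongest reply is that the SAP saw the problem and dealt with it by excluding later bottles. That stands in part. A reader might infer that all tablets taken after failure are counted; the bottle exclusion contradicts this, and it removes the error for failures first seen at Weeks 4 and 8, including the Week 8 nonresponse criterion. It does not reach bottles dispensed earlier. Its wording also does not literally cover RBV, which comes in blister packs (Protocol 5.4.2).

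A reader might also infer larger errors by assuming perfect dosing during a full 14-day lag. The threshold for a reported 100% is then (d − 14)/d: 60% at Week 5, 66.7% at Week 6 and 80% at Week 10. The documents do not support this as the expected case. Two weeks is the outer limit for a confirmation that is to be done as soon as possible, and nothing suggests that poor adherers start dosing perfectly.

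Nor does the section always overstate adherence: the unreturned-bottle rule biases it downward. That is a separate error and does not correct this one.

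Finally, adherence is descriptive, and SAP 4.2.2 promises a by-subject, by-visit accountability listing, so a reader could check each failure by hand. This limits the harm but leaves the tabulated value wrong.

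**Conclusion.** The point holds in a limited form. The stated rule gives numerator and denominator different end dates when the first failing sample falls between dispensing visits. It can then report a subject below the SAP's own 80% cut as 80% or more, or even as 100%. The clearest case is Week 6 with a 14-day lag and constant adherence: 75% becomes 100%, and 60% becomes 80%. These sizes rest on the assumptions listed and shrink with a shorter lag.

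The practical weight is small. A subject must stop for on-treatment virologic failure, be imperfectly adherent, be first seen failing away from Weeks 4 and 8, and wait long enough for confirmation. The cited data suggest few such subjects, though for LDV/SOF they are sparse. A reader might infer that the trial's efficacy conclusion is at risk. It is not: the primary non-inferiority analysis does not use adherence, and only the descriptive adherence tables and one exploratory SVR12 subgroup are affected. This is a clarification worth making before database finalization.

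**What to change.** In SAP 4.2.2, for subjects who stop for virologic failure, count tablets administered only up to the date of the first failing sample, using the pill count made at that visit, and word the rule to cover RBV blister packs as well as bottles. Reported adherence then equals adherence up to failure: in the Week 6 example with 75% adherence, 31.5/42 = 75%.

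If that visit's count is unavailable, run both numerator and denominator to the last dose date, which SAP 3.8.1 already defines, and footnote that post-failure dosing is included. This is second best because that dosing can itself move a subject across the cut. For example, 31 of 42 tablets before failure (73.8%) followed by 14 of 14 gives 45/56 = 80.4%. Showing uncapped values in the listing would make any remaining mismatch visible.

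The cost is a sentence or two in the SAP, a small programming change, and reliance on visit-level pill counts, whose storage on the CRF should be confirmed. Study conduct does not change.
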